**\*VALID ONLY AS LONG AS APPROVED PROCEDURES ARE FOLLOWED\***

**V. TYPE OF NEW SUBMISSION**  IRBshare**MINIMAL RISK** (The research meets the **definition of minimal risk** and falls into one or more expedited review categories. You are done with this table.)  **FULL COMMITTEE**

- Full Committee (The research involves **greater than minimal risk** and requires review at a convened meeting of the IRB)
- Full Committee (The research involves **no more than minimal risk** but does not fit into one of the expedited review categories)

**METHODS:**

Please mark the boxes to indicate the methods which best describe your study:

**Social-Behavioral Procedures/Considerations**

  Observational	  Population-Based Field Study
  Behavioral Interventions	  Surveys/Questionnaires
  Interview/Focus Groups	  Other – Describe:

**Medical Procedures/Considerations**

  Bio-hazardous Substances	  Investigational/Approved Devices
  Controlled Substances	  Radiation Exposure
  Emergency Treatment	  Substance Abuse Treatment (with medication)
  Gene Transfer Study	  Surgical Procedures
  Stem Cell Research	  Genetic Testing
  Magnetic Resonance imaging (MRI)	  Complementary/Alternative Medicine
  Investigational/Approved Drugs and Biologics	  Other – Describe:

**DOES YOUR RESEARCH INVOLVE OR IS IT ASSOCIATED WITH ANY OF THE FOLLOWING:**

- Emergency Medicine
- Pregnant Women as a Target Population
- Genetics
- Stem Cells
- Neuroscience
- College of Arts and Sciences
- College of Education
- Dentistry
- Infectious Disease
- HIV/AIDS
- Psychiatry
- Rehabilitation Medicine
- Psycho-Social Drug Abuse Research
- Alaska Native/American Indian (ANAI)
- Public Health
- Global Health
- Health Services
- Quality of Care / Quality of Life
- Health Prevention / Health Education
- Nursing

**VI. PRIMARY RESEARCH ROLES**

Some research projects are conducted by a large team of individuals. Other projects can be performed by only one or two individuals. The IRB does not need to know the name of every member of your research team - instead, the IRB wants to know who is fulfilling

the following specific roles for your research. Note that the same individual may play multiple roles. If it is necessary to identify an individual by name, this will be specified below. Each section below must be completed.

**1. Information for individuals identified by name:**

The individuals below need to be identified by name. If these individuals change during the course of the research, a Modification approval from the IRB is needed before making the change.

**2. Information for research staff who will perform procedures that involve risk to subjects:**

The individuals below do not need to be identified by name, rather, by qualifications. As long as the qualifications of the individuals and the procedures performed remain the same, a modification is not needed.

If an individual is **not** an agent of the UW, indicate his/her institution or organization. Should an individual not be associated with an institution or organization, state so. For all non-UW individuals, it will be necessary for this individual to receive IRB review. There are a number of mechanisms by which this may occur.

- If the non-UW individual is associated with Pacific Northwest National Laboratories, Puget Sound Blood Center, King County-Seattle Public Health, or Northwest Kidney Center: the UW has an institutional Authorization Agreement with these institutions by which it provides the IRB review (as long as any funding is administered through the UW).
- If the non-UW individual is associated with the Fred Hutchinson Cancer Research Center, Group Health, Seattle Children's, Swedish Medical Center, or Benaroya Research Institute at Virginia Mason: the terms of the UW's Cooperative IRB Agreement with these institutions may or may not allow the UW IRB to do the review. The individual should contact their institution's IRB for guidance.

- If the non-UW individual is associated with an institution or organization in which the UW does not have a Cooperative IRB Agreement, it will be necessary for the non-UW individual to provide their own IRB review. If the non-UW individual's institution or organization does not have their own IRB or does not use an IRB for review of their research and the non-UW individual's institution or organization has a Federalwide Assurance (FWA), the non-UW individual's institution or organization may enter into an **IRB Authorization Agreement** with the UW. This means that the UW will provide IRB review for the non-UW individual. The non-UW Individual's institution or organization may also wish to enter into an IRB Authorization Agreement even if they have their own IRB to prevent duplication of effort. However, entering into an IRB Authorization Agreement with a non-UW individual's institution or organization is at the discretion of the HSD.
- If the non-UW individual is not associated with an institution or organization or if the non-UW individual is associated with an institution or organization that does not have a FWA and does not routinely conduct research, an **Individual Investigator Agreement** may be entered into with the UW. The Individual Investigator Agreement extends the applicability of the UW's FWA to cover the non-UW individual, institution or organization. However, entering into an Individual Investigator Agreement with a non-UW individual, institution or organization is at the discretion of the HSD.

Please see [SOP Authorization Agreements](#) for information on how to obtain an Agreement for your research.

#### **Study Procedures that involve risk to subjects**

**Phlebotomy (blood draw)**

Who will perform this procedure?

**Licensed Practitioner**

Describe the qualifications for the Licensed Practitioner below, including whether they are affiliated with the UW, any requirement for professional license or credential, and/or experience in performing this procedure:

**Study Nurse**

Describe the qualifications for the Study Nurse below, including whether they are affiliated with the UW, any requirement for professional license or credential, and/or experience in performing this procedure:

**Other:**

Describe the qualifications for the Other Professional below, including whether they are affiliated with the UW, any requirement for professional license or credential, and/or experience in performing this procedure:

**MRI Scan**

Who will perform this procedure?

**Licensed Practitioner**

Describe the qualifications for the Licensed Practitioner below, including whether they are affiliated with the UW, any requirement for professional license or credential, and/or experience in performing this procedure:

**Study Nurse**

Describe the qualifications for the Study Nurse below, including whether they are affiliated with the UW, any requirement for professional license or credential, and/or experience in performing this procedure:

**Other:**

Describe the qualifications for the Other Professional below, including whether they are affiliated with the UW, any requirement for professional license or credential, and/or experience in performing this procedure:

**Surgical or Physically Invasive Procedure**

Who will perform this procedure?

**Licensed Practitioner**

Describe the qualifications for the Licensed Practitioner below, including whether they are affiliated with the UW, any requirement for professional license or credential, and/or experience in performing this procedure:

**Study Nurse**

Describe the qualifications for the Study Nurse below, including whether they are affiliated with the UW, any requirement for professional license or credential, and/or experience in performing this procedure:

**Other:**

Describe the qualifications for the Other Professional below, including whether they are affiliated with the UW, any requirement for professional license or credential, and/or experience in performing this procedure:

**Other Procedures Involving Risk to**

Subjects [name the procedure(s)]:

*Examples: behavioral therapy; dietary counseling; assessments and/or interpretations of test results that require specific expertise (e.g. physical exam; fitness assessment; cognitive state; suicidality; mental health; interpretation of imaging tests, genetic tests, cognitive tests, etc.)*

*For more than one "Other" procedures, copy and paste this portion of the table as many times as necessary.*

Who will perform this procedure?

Licensed Practitioner

Describe the qualifications of the Licensed Practitioner below, including whether they are affiliated with the UW, what is their professional license, and their experience in performing this procedure:

Study Nurse

Describe the qualifications of the Study Nurse below, including whether they are affiliated with the UW, what is their professional license, and their experience in performing this procedure:

Other:

Describe the qualifications of the Other Professional below, including whether they are affiliated with the UW, what is their professional license, and their experience in performing this procedure:

**3.a. Non-UW Individuals, Institutions or Organizations.** It will be necessary for each non-UW individual, institution or organization listed below to receive IRB review of its involvement in this research. There are a number of mechanisms by which this may occur.

**Please only list the non-UW individual, institution or organization below if you are:**

- The direct recipient of an award or if you will be providing funding to the non-UW individual, institution or organization through a mechanism such as a sub-contract; and
- If the non-UW individual, institution or organization will be acting on behalf of the UW research study to do any of the following: 1) Obtain consent from subjects, 2) Perform procedures involving subject interaction or observation, 3) Obtain identifiable data/specimens, 4) Have access to, or receive coded or identifiable data/specimens, 5) Intervene by manipulating the environment.
- If the non-UW individual is associated with Pacific Northwest National Laboratories, Puget Sound Blood Center, King County-Seattle Public Health, or Northwest Kidney Center: the UW has an institutional Authorization Agreement with these institutions by which it provides the IRB review (as long as any funding is administered through the UW).
- If the non-UW individual is associated with the Fred Hutchinson Cancer Research Center, Group Health, Seattle Children's, Swedish Medical Center, or Benaroya Research Institute at Virginia Mason: the terms of the UW's Cooperative IRB Agreement with these institutions may or may not allow the UW IRB to do the review. The individual should contact their institution's IRB for guidance.
- If the non-UW individual, institution or organization is one in which the UW does not have a Cooperative IRB Agreement, it will be necessary for the non-UW individual, institution or organization to provide their own IRB review. If the non-UW individual, institution or organization does not have their own IRB or does not use an IRB for review of their research, and the non-UW individual, institution or organization has a Federal Wide Assurance (FWA), the non-UW individual, institution or organization may enter into an IRB Authorization Agreement with the UW. This means that the UW will provide IRB review for the non-UW individual, institution or organization. The non-UW individual, institution or organization may also wish to enter into an IRB authorization Agreement even if they have their own IRB to prevent duplication of effort. However, entering into an IRB Authorization Agreement with a non-UW individual, institution or organization is at the discretion of the HSD.
- If the non-UW individual is not associated with an institution or organization that has a Federal Wide Assurance (FWA) or if the institution or organization listed below does not have a FWA and does not routinely conduct research, an Individual Investigator Agreement may be entered into with the UW. The Individual Investigator Agreement extends the applicability of the UW's FWA to cover the non-UW individual, institution or organization. However, entering into an Individual Investigator Agreement with a non-UW individual, institution or organization is at the discretion of the HSD.

Please see SOP Authorization Agreements for information on how to obtain an Agreement for your research.

3b. Non-UW Individual, Organization or Location:

*If there is more than one non-UW individual, organization, or location, copy and paste this table as many times as necessary.*

Name of the non-UW Individual, Organization or Location:

Address of the non-UW Individual, Organization or Location:

Describe the activities that will be performed by/at the non-UW Individual, Organization or Location (if the specified activities will not be performed, please enter N/A):

Obtain consent from the subjects:

Perform procedures involving subject interaction or observation:

Obtain identifiable data/specimens?

Have access to, or receive coded or identifiable data/specimens:

Intervene by manipulating the environment:

**VII. SECTION 1 - LIST EACH PROPOSED AND FUNDED GRANT OR CONTRACT RELEVANT TO THIS APPLICATION, AND ATTACH A COMPLETE COPY OF EACH GRANT OR CONTRACT. THIS SHOULD INCLUDE GRANTS THAT SUPPORT FACULTY TIME FOR DATA ANALYSIS AND MANUSCRIPT PREPARATION, (I.E. SALARY SUPPORT). IF NONE, CHECK HERE  FOR CENTER OR PROGRAM PROJECT GRANTS LIST P.I. AND TITLE FOR EACH SEPARATE PROJECT OR CORE. ADD SHEETS IF NECESSARY.**

For Center, Program, and Institutional Training Grants (e.g., NIH "P" awards and "T" awards): Attach only the following components of the application. The terms used here are from the standard NIH applications for these types of grants. If the grant is from another agency, provide the equivalent application sections.

- Cover page(s)
- Project/Performance Site Location
- Other Project Information
- Research Plan (for Center or Program grants)
- Research Training Program Plan (for Institutional Training grants)
- Biosketch (profile) for the principal investigator on the grant

For Department of Defense (DOD) funding, complete and attach the SUPPLEMENT: Department of Defense  
For Department of Justice (DOJ) funding, complete and attach the SUPPLEMENT: Department of Justice

A. Type of proposal:  Research  Contract  Fellowship  Training grant  Subcontract  
 Other, specify

B. Name of principal investigator: [name]

C. Name of funding agency: Royalty Research Fund

D. Agency's number (if assigned): A97186

E. Title of proposal: Endurance, energy expenditure, perceived function, and satisfaction of persons with transtibial limb loss using a running-specific prosthesis modified for walking

F. Inclusive dates: from 03/01/15 through 04/30/16

G. Status:  New  Competing renewal  Non-competing renewal

H. Submitted through UW Office of Sponsored Programs?  Yes  No, (attach explanation)

---

**VIII. SUMMARY OF ACTIVITY.** Answer in spaces provided (add numbered, referenced, single-sided sheets when necessary). Do not refer to an accompanying grant or contract proposal.

**A. BACKGROUND AND PURPOSE OF RESEARCH.** Provide relevant background information and explain in lay language why this research is important and what question(s) or hypotheses this activity is designed to answer.

Amputation of a limb is a life-altering event with profound physical, psychological, and social implications. To address their functional, vocational, and recreational needs, people with lower limb amputation (LLA) are often provided with a prosthesis or artificial leg. While use of a prosthesis can allow an individual to achieve a basic level of functional mobility, absence of an anatomical foot and ankle still impairs their physical performance. As a result, people with LLA regularly exhibit decreased walking speeds, diminished endurance, and restricted ability to participate in desired life situations.

Over the past three decades, increasingly sophisticated prosthetic foot designs have been developed by the prosthetics industry to replace amputated structures in the leg. Contemporary, energy storing feet (ESF) employ advanced materials and unique geometric designs to improve walking performance and endurance of their users. Although prosthetic limbs with ESF allow people with LLA the potential to return to an active lifestyle, even the most advanced ESF do not significantly reduce the increased energy demands required for walking when compared to conventional prosthetic feet.

Commercially-available running-specific feet (RSF) like the Össur Cheetah (Össur, Reykjavik, Iceland) allow people with LLA to participate in athletic activities and sporting events. RSF provide significantly enhanced performance, compared to traditional ESF, by extending the length and increasing the stiffness of the prosthetic keel (forefoot). RSF also do not include a heel, as they are used only for running activities. Although transtibial runners with RSF exhibit endurance levels similar to non-amputees, the RSF design does not allow the biomechanical movements or provide the stability needed to use the foot for walking (over level or uneven terrain).

A Seattle-area prosthetist, [name], currently provides many of his active LLA patients with a modified running-specific foot (mRSF). The mRSF combines the running keel (forefoot) of a RSF with the walking heel of a ESF. The mRSF can then be used for walking, running, and other routine daily activities. [name] has fit and provided this prosthetic foot on over 100 of his patients. Preliminary feedback suggests that users experience improved overall function and high satisfaction with the device. However, empirical evidence is needed to support prescription of this prosthetic foot at other clinical facilities. The goal of this study is therefore to evaluate endurance, walking performance, mobility, and perceived exertion of transtibial prosthesis users (i.e., study participants) walking with a conventional ESF and the mRSF. Results will be compared to determine if the mRSF provides superior performance to the ESF, which is commonly prescribed to most active individuals with LLA.

**Hypotheses:**

- 1a. Participants with LLA will exhibit significantly increased endurance (as evidenced by an ability to walk significantly further in a timed walking test) wearing the mRSF compared to the ESF.
- 1b. Participants will report significantly reduced levels of exertion after performing a timed walking test in the mRSF, compared to the ESF.
- 2a. Participants will report significantly increased mobility, balance confidence, and health and significantly decreased fatigue when using the mRSF, compared to the ESF.
- 3a. Use of the mRSF will significantly reduce participants' net energy cost of walking (ECW) at slow, comfortable, and fast walking speeds, compared to the ESF.

**B. RESEARCH PROCEDURES INVOLVED.**

1. Provide a complete description of: a. the study design, and b. sequence and timing of all study procedures that will be performed, e.g., volume of blood, size of biopsy, drug administration, questionnaire, name of psychological test. Provide this information for each phase of the study (pilot, screening, intervention and follow-up). **Use lay language.** Attach study flow sheet, if available.

We will conduct a study to compare endurance, walking performance, mobility, and perceived exertion of participants with transtibial amputation wearing two different prostheses: (1) a prosthesis with a modified Running Specific Foot (mRSF), and (2) a prosthesis with a Energy Storing Foot (ESF). To maximize study resources, we will recruit participants who will be receiving from their prosthetist the mRSF prosthesis as part of their normal clinical care. We will fabricate a duplicate prosthesis with the ESF as part of this study to be used as a comparison.

*Note: Both the mRSF and ESF included in this study are devices that people with LLA use daily in their normal lives outside of this study. These feet (and other components included in the prostheses created for this study) are class I devices and exempt from U.S. Food and Drug Administration premarket notification procedures.*

We will conduct a randomized crossover study to compare endurance, energy expenditure, and reported health of participants with transtibial amputation wearing prostheses with the mRSF and ESF described above. Study participants will be randomly assigned to the first foot condition (i.e. ESF or mRSF). To standardize test conditions, the participant's prosthetist ([name]) will fabricate two comparable prostheses with identical (i.e. duplicated) prosthetic sockets, interfaces, and suspension mechanisms. The same socket cannot be used for both prostheses because of the unique, direct-lamination attachment of the mRSF to the socket. The duplicate socket will be fitted with common ESF, the Ossur Vari-flex foot. We have obtained written commitments from Ossur to donate prosthetic components and from Davidson Prosthetics to donate time and materials needed to fabricate the duplicate sockets and test prostheses. Participants will be asked to wear the same athletic shoes for all sessions in order to standardized footwear between tests.

Participants will be recruited from their local prosthetist's office (Davidson Prosthetics, Federal Way, WA). Davidson Prosthetics is the sole location for recruitment as this is the only provider of the mRSF in the Northwestern United States.

Participants will be asked to come to the University of Washington Assessment and Training Laboratory (ATL) for three test sessions. Participation in the study will require participants attend three visits over the course of about three months, totaling approximately 7.5 hours.

Session 1: At the first session, we will screen participants, explain the study to them, and obtain informed consent (**Appendix 1**). Participants who agree will then be administered a baseline survey and perform initial speed testing. The baseline survey will include non-identifiable, medical, and demographic questions we will use to characterize the study sample (**Appendix 2**). Participants will then be asked to walk on a treadmill for 6 minutes to determine their comfortable walking speed. The treadmill is equipped with full-length handrails that allow the participant to steady him/herself as needed. A researcher will be next to the subject at all times to assist the subject if he or she were to become distressed.

Participants will be given blinded control of the treadmill speed for the first 30 seconds of testing in order to select their preferred speed. Each participant's comfortable speed will be noted and used as a reference for the metabolic testing (see Session 2 and 3, described below). Slow and fast speeds will be self-selected using an identical method (blinded control of the treadmill adjustment). Participants will be asked to perform a 6 minute practice trial at their self-selected fast speed to ensure the participant is capable of sustaining the speed without undo stress. If a participant is unable to sustain the set speed for the entire 6 minutes, he/she may reduce speed as desired, and a weighted average of the start and end fast speeds will be used for treadmill testing in Sessions 2 and 3. We will also give participants a step activity monitor to wear on their prosthesis. The activity monitor is a small, unobtrusive sensor about the size of a pager that is worn on the prosthesis and measures steps taken by the participant while they are away from the lab. Participants will be shown how to attach the activity monitor to their prosthesis by study investigators. Session 1 is expected to take about 1.5 hours.

Session 2: The second session will be performed after participants use the randomly-assigned ESF or mRSF prosthesis for a period of 1 month. Upon arrival at the lab, study

staff will remove the activity monitor and ask the participant to complete a self-report survey (**Appendix 2**) to evaluate their perceived performance, health, and satisfaction with their prosthesis. The survey will be administered on a tablet computer (iPad) and includes the following standardized instruments selected to measure participants' mobility, fatigue, balance confidence, activity restrictions, and satisfaction:

- Prosthetic Limb Users Survey of Mobility - PLUS-M measures respondents' self-reported mobility with a prosthesis. The PLUS-M was developed by the investigators in a prior study to address methodological limitations present in existing mobility measures. We will administer the PLUS-M computer adaptive test (CAT) to achieve the greatest precision of measurement and ease respondents' burden (i.e., CAT requires participants answer fewer questions than would taking the entire survey).
- PROMIS - Fatigue - PROMIS-F measures symptoms and effects of fatigue on respondents' ability to execute daily activities over a 1-week recall period. We will also administer PROMIS-F by CAT.
- Activities Specific Balance Confidence Scale - ABC measures respondents' confidence in performing basic ambulatory activities. We will administer a version of the ABC recommended to ease administration and improve scoring. All 16 questions of the ABC will be administered (CAT not available).
- Trinity Amputation and Prosthesis Experience Scales - Revised - TAPES-R is a multidimensional health instrument that measures activity restrictions and satisfaction with a prosthesis. We will administer 19 TAPES-R questions (CAT not available).

We will next assess participants' walking performance and endurance using the 6-minute walk test (6MWT). The 6MWT is a sub-maximal test of aerobic capacity and endurance that exhibits good test-retest reliability in transtibial prosthesis users. The 6MWT will be conducted using a 100ft unobstructed indoor hallway, in accordance with recommended administration guidelines. During the 6MWT, participants will walk back and forth over a pressure-sensitive instrumented mat placed in the middle of the hallway. The mat will collect outcomes associated with walking such as step length, step width, walking speed. Upon conclusion of the 6MWT, participants will self-report their exertion using the Borg Rating of Perceived Exertion (RPE). The Borg RPE measures participants' perceived exertion after completing a standardized physical test. Note, participants will perform the 6MWT after evaluation of resting O2 consumption (see below) but before the treadmill testing so as to ensure baseline O2 consumption is not adversely affected by the 6MWT.

To assess the effects of the studied prosthetic feet on energy cost of walking, we will measure participants' real-time metabolic energy expenditure (i.e., O2 consumption) across three walking speeds (slow, comfortable, fast). The gold standard method for determining energy consumption is measurement of the amount of oxygen a person intakes (VO2) and carbon dioxide that a person expires (VCO2). We will measure VO2 and VCO2 using a portable Cosmed K4b2 monitor. The K4b2 monitor continuously samples the participant's expiration and inspiration using a mask that fits over their nose and mouth. Plastic tubes convey the gases to sensors that are located in a small, lightweight (1 lb) backpack system. Breath-by-breath measurements of the expired gases are stored in the system until they are uploaded by the researcher to a laptop after the experiment is completed.

Participants will be fitted with the K4b2 monitor upon conclusion of the self-report survey (described above). They will sit quietly for 5 minutes to achieve steady-state resting VO2 consumption rate (ml/min). Resting VO2 rate will be quantified as an average over the final minute of resting. Participants will then stand for 5 minutes to achieve a standing VO2 consumption rate (ml/min), again averaged over the final minute of standing.

Participants will remove the K4b2 monitor and conduct the 6MWT according to the protocol described above. After completing the Borg RPE, the participant will re-don the K4b2 monitor and sit quietly in order to return to their resting VO2 rate.

Participants will begin the treadmill testing once they have returned to their resting VO2 rate.

Participants will walk for 6 minutes on the treadmill at comfortable, slow, and fast walking speeds (as determined in Session 1). The order of the speeds will be randomized within-subjects to control for fatigue. This randomized order will be carried over into the third session so that participants are tested in the same order both times. Walking VO2 consumption rate (ml/min) will be averaged over the final 1 minute period of each activity. Participants will rest at least 5 minutes between each walking trial in order to return to their resting VO2 rate.

Session 2 will require about 3.0 hours to complete. Upon conclusion of Session 2, participants will transition to the second prosthesis (ESF or mRSF, depending upon randomization) and will be asked to use it exclusively for 1 month before returning for Session 3.

Session 3: The third session will be identical to the Session 2, but will be conducted with participants using the alternate prosthesis (e.g., ESF if they were previously tested in the mRSF).

2. Would subjects undergo these or similar procedures (medical, psychological, educational, etc.) if they were not taking part in this research?  No  Yes If "Yes," describe how the study procedures differ from what subjects would otherwise undergo.

The study procedures include outcome measures (survey measures, 6MWT, or Borg RPE) that a prosthetist might perform in a clinic to evaluate a patient's performance with a new prosthesis. However, the Cosmed K4b2 portable metabolic analysis system and treadmill walking are unlikely to occur in normal prosthetic clinical practice. These procedures are more likely to be conducted as part of a physical therapy treatment plan and would not be considered unusual procedures at a physical therapy clinical visit.

3. Check all of the boxes below that apply to your research:

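### Do the differing outcome lists in the goal and design paragraphs leave the superiority conclusion unfixed?

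*Protocol*

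**What the plan says.** Section VIII.A gives the goal as to "evaluate endurance, walking performance, mobility, and perceived exertion of transtibial prosthesis users" and adds: "Results will be compared to determine if the mRSF provides superior performance to the ESF". The first paragraph of section VIII.B repeats that list: the study will "compare endurance, walking performance, mobility, and perceived exertion of participants with transtibial amputation wearing two different prostheses". A later paragraph of the same section, which introduces the randomized crossover, says it is "to compare endurance, energy expenditure, and reported health of participants with transtibial amputation wearing prostheses with the mRSF and ESF".

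Between these stand the numbered hypotheses, each with a direction and a comparator:

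- 1a: distance in a timed walk.
- 1b: exertion after that walk.
- 2a: "Participants will report significantly increased mobility, balance confidence, and health and significantly decreased fatigue when using the mRSF".
- 3a: net energy cost at three walking speeds.

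None is called primary. In the Session 2 description, PLUS-M measures mobility, PROMIS-F fatigue and ABC balance confidence. TAPES-R is described as a "multidimensional health instrument that measures activity restrictions and satisfaction with a prosthesis".

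**The concern.** A reader who takes each summary as a definition of the endpoints finds two definitions. Energy cost is missing from the goal list, and exertion is missing from the crossover list. Balance confidence and fatigue are named in neither, although both are in hypothesis 2a. The word *performance* in the superiority sentence is tied to no single measure, and no instrument is said to give a score for *health*.

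The stake would be a conclusion that depends on which sentence is followed. The background supplies a possible case. It describes feet designed for better walking performance and endurance, yet says that "even the most advanced ESF do not significantly reduce the increased energy demands required for walking". If the mRSF improved walking but not energy cost, the goal list would read as success and the crossover list as mixed. With several outcomes and no lead, a favourable result could also be picked out after the fact.

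**Working it through.** **1. The lists side by side**

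| Outcome named | Goal (VIII.A) and opening of VIII.B | Crossover sentence (VIII.B) | Hypotheses |
|---|---|---|---|
| Endurance | yes | yes | 1a |
| Walking performance | yes | no | none of its own |
| Mobility | yes | no | 2a |
| Perceived exertion | yes | no | 1b |
| Energy expenditure | no | yes | 3a |
| Reported health | no | yes | 2a |
| Balance confidence | no | no | 2a |
| Fatigue | no | no | 2a |

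By name, the two lists hold 4 + 3 − 1 = 6 different items and share one. The goal and the opening of VIII.B are identical, so the only mismatch is with one later sentence in VIII.B.

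**2. How far the count of 1 in 6 depends on the reading**

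The Session 2 text uses the 6-minute walk test for both walking performance and endurance, although an instrumented mat adds gait measures. The self-report survey as a whole is introduced as covering perceived performance, health and satisfaction, so *reported health* can be shorthand for that survey, which contains the mobility instrument. On that reading the items become the walk test, the survey, exertion and energy cost. The lists then share 2 of 4. Exertion and energy cost still stand on one side only, but both have their own hypothesis (1b and 3a) and their own measurement procedure.

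**3. The chance of a spurious favourable result**

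The protocol states no test level and no decision rule. Assume that each comparison is tested at two-sided 5%, so 2.5% in favour of the mRSF, that any favourable result counts as superiority, and that the tests are independent. With no true difference, the chance of at least one favourable result in k comparisons is 1 − 0.975^k.

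- k = 1: 2.5%.
- k = 3 (goal list matched to hypotheses: distance, exertion, mobility): 1 − 0.9269 = 7.3%.
- k = 5 (crossover list: distance, one health score, energy cost at three speeds): 1 − 0.8811 = 11.9%.
- k = 9 (all hypotheses: 1 + 1 + 4 + 3): 1 − 0.7962 = 20.4%.

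At an assumed correlation of 0.5 between all outcomes, the values for 3, 5 and 9 are 6.3%, 9.1% and 13.5%.

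**4. What these figures depend on**

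The 20.4% comes from the nine comparisons in the hypotheses. Rewriting both summaries to match the hypotheses would leave k = 9 and the same 20.4%, so the figure does not measure the effect of the inconsistent lists. The any-result rule is also an assumption. Hypotheses 2a and 3a join their components with *and*. If each had to hold in full, there would be four claims, each with a chance of at most 2.5% under no difference. The chance of any one succeeding would then be at most 4 × 2.5% = 10%, or at most 1 − 0.975^4 = 9.6% if the claims are independent.

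**5. Whether hypothesis 2a can be tested**

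Three of its four components have a named instrument: mobility, balance confidence and fatigue. Only *health* does not. TAPES-R is the one instrument described in health terms, but its stated content is activity restriction and satisfaction.

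**The case for a change.** The strongest case for a change is that a protocol should carry one consistent list of outcomes and name the primary one, because an analysis plan written later inherits any conflict. Endurance appears in both lists, in the hypotheses and in the grant title, and it has a defined measure, so naming 6-minute walk distance as the lead would cost only words. *Health* would still lack a score even if the lists were read generously.

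Part of this stands: no hypothesis is marked primary, and one word in 2a has no named score. The rest does not carry the change. Making walk distance the lead and treating the other outcomes as supportive would be more than wording. Energy cost is a full hypothesis with the most elaborate measurement in the study, and it is in the grant title too. Lowering its rank is a scientific choice on which reasonable statisticians would differ. The energy scenario is an analogy: the background sentence compares ESF with conventional feet, not the mRSF with the ESF. If energy cost did not improve, hypothesis 3a would be unsupported whichever summary sentence was followed.

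**Conclusion.** No change to the plan follows. The summary sentences are untidy, but neither says that an outcome is excluded, and the section asks for lay language. The hypotheses are the operative statement. Each one, tested as written, answers its own question, and aligning the summaries would alter no result.

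The two remaining gaps are small. In a study that calls itself a pilot, with at most 24 completers, reporting all four hypotheses is a fair course, and an analysis plan, which is not at hand, may rank them. The score that stands for *health* needs only to be written down before analysis. It affects one of nine comparisons.

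This rests on reading the hypotheses as governing and the lists as descriptive. A document that declared superiority on any single favourable outcome would deserve a different answer, because the 20.4% (13.5% at correlation 0.5) would then apply. This one does not say so.
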